2.1.2 Statistical Hypotheses

The primary endpoint, CMAP total amplitude at Week 28, measured as percentage relative to baseline (%), will be analysed using a Mixed-effects Model for Repeated Measures (MMRM), $\delta_{db} = \mu_{dysport} - \mu_{botox}$ and $\delta_{dx} = \mu_{dysport} - \mu_{xeomin}$ are the contrasts (i.e. mixed model Wald tests) of the Dysport versus Botox versus Xeomin comparisons in the primary endpoint at Week 28 of the study. Two elemental null hypotheses will be investigated,

$$H_{0,db,1} : \delta_{db} = 0 \text{ and}$$

$$H_{0,dx,1} : \delta_{dx} = 0.$$

These null hypotheses of no difference between the respective treatment arms in the primary endpoint will be tested against the respective two-sided alternative hypotheses

$$H_{A,db,1} : \delta_{db} \neq 0 \text{ and}$$

$$H_{A,dx,1} : \delta_{dx} \neq 0$$

at a 5% significance level ($\alpha = 0.05$) using a MMRM model and mixed model Wald tests of the respective contrast the Dysport versus Botox versus Xeomin comparisons in the primary endpoint at Week 28 of the study.

To control for the family-wise type I error rate at the two-sided level $\alpha = 0.05$, a Hochberg procedure [Dmitrienko and D'Agostino 2013] will be applied to investigate the two null hypotheses $H_{0,db,1}$ and $H_{0,dx,1}$. The testing procedure uses the following decision rules for the two p-values p_{db} and p_{dx} :

- Both null hypotheses are rejected if $\max(p_{db}, p_{dx}) \leq \alpha$
- Only the null hypothesis corresponding to the smaller p-value $\min(p_{db}, p_{dx})$ is rejected if $\min(p_{db}, p_{dx}) \leq \alpha/2$ and $\max(p_{db}, p_{dx}) > \alpha$.

If both null hypotheses of the primary endpoint are rejected, then the same Hochberg procedure will be applied sequentially to the two respective null hypotheses comparing Dysport with Botox and with Xeomin for secondary endpoints in the following order:

- CMAP total amplitude at Week 40 post-injection
- Incidence of recovery of CMAP total amplitude at Week 28 post-injection
- Incidence of recovery of CMAP total amplitude at Week 40 post-injection

The two null hypotheses of secondary endpoint k, k =2, 3 are tested with a Hochberg procedure, when both null hypotheses of endpoint k-1 are rejected.

2.2 Overall Study Design and Investigational Plan

[figure not shown]
This is a phase I, randomised, double-blind, parallel-group, single-centre comparative study to evaluate the pharmacodynamic profile of Dysport 40 U, Botox 16 U and Xeomin 16 U in the EDB model in healthy adult male participants.

A total of 45 participants will be randomised in a balanced ratio of 1:1:1 to Dysport 40 U, Botox 16 U or Xeomin 16 U to be administered as a single injection on Day 1.

The maximum duration of the study is anticipated to be approximately 10 months from screening to last study visit. The participants will be followed-up for 40 weeks.

The study design is illustrated in [Figure 1](#).

Figure 1 Study Schema

D=day; W=week; V=visit.

2.3 Sample Size Determination and Power

It was anticipated that approximately 48 participants are planned to be screened to achieve 15 participants randomised to Dysport, 15 participants randomised to Botox and 15 participants randomised to Xeomin using a 1:1:1 randomisation ratio and assuming a screening failure rate of 5%.

The sample size calculation is based on the primary efficacy estimand and its endpoint relative change from baseline in EDB CMAP total amplitude at Week 28. Using a 2-sided t-test at the 5% significance level, the chosen sample size provides at least 88% power to detect a treatment difference of 18% relative change from baseline in the Dysport arm than in a comparator arm assuming a common Standard Deviation (SD) in all treatment arms of 15% as observed for Dysport in a legacy study [CCI](#) – Part B. The treatment difference is based on the observed average EDB CMAP total amplitude at 6 months of Dysport 40 U ([CCI](#) – Part B) and of Botox and Xeomin 16 U in Wohlfarth [[Wohlfarth 2007](#)]. The power analysis was conducted with NQuery version 8.4.1.0. Given the made assumptions and the sample size of 15 participants per arm the probability to show superiority of Dysport to both comparators simultaneously is at least 81%, as shown in a simulation study conducted with software R version 4.0.3.

2.4 Randomisation and Blinding

The sponsor's randomisation manager who is a statistician independent of the study will prepare the list of randomisation numbers for this study. It will be produced in blocks, on a balanced ratio [1 Dysport: 1 Botox: 1 Xeomin].

Recruitment will stop once 45 participants have been randomised.

Randomised participants who discontinue the study early will not be replaced.

During the study, the sponsor, investigator (including study site personnel) and the participant will be blinded to the study intervention. To maintain the blind during the study only a qualified, trained and unblinded person independent of the injector and investigator will prepare (i.e. reconstitute) the study intervention and will have no further involvement in the study.

Due to slight differences in colour between the study interventions and to maintain the blind during the study, the injector will also be independent from the investigator and be unblinded (note: the injector will be different from the person who will evaluate CMAP). Following injection of the study intervention, the injector will have no further involvement in the study.

For more details to randomisation and blinding, please refer to the section 6.3 of the protocol.

2.5 Schedule of Activities

Schedule of activities is presented in section 1.3 of the protocol.

2.6 Change from Statistical Section of the Protocol

No change from statistical section of the protocol has been done, only clarifications have been made:

- The wording of the primary endpoint has been updated from "CMAP total amplitude relative change from Baseline (%)" to "CMAP percentage relative to baseline (%)".
- The following secondary endpoints: CMAP total amplitude at Week 40, incidence at Week 28 of recovery of CMAP total amplitude and incidence of recovery of CMAP total amplitude at Week 40, for which the alpha risk is controlled, are considered as key secondary endpoints.
- The definition of the time to onset of action has been updated from "Time to onset of action is defined as the first timepoint where EDB CMAP total amplitude is 85% or lower than the Baseline value" to "time to onset of action is defined as first timepoint where EBD CMAP total amplitude is less or equal to 85% of the baseline value".

3 PLANNED ANALYSES

3.1 Data Monitoring

No independent Data Monitoring Committee will be used in this study.

3.2 Interim Analysis / Primary Analysis

No interim analysis will be performed.

3.3 Final Analysis

Planned analyses will be done when all participants complete study and after database lock.

4 ANALYSIS SETS

Screened Set

The screened set will contain all participants who signed an informed consent for this study.

Randomised Set

The randomised set will contain all participants who were randomised to study treatment. A participant will be considered as randomised if a study intervention group has been randomly assigned. For analyses and displays, participants will be classified according to randomised treatment.

Safety Set

The safety set will contain all participants who receive at least one dose of study medication. For analyses on the safety set, participants will be classified according to treatment received. If

there is any doubt whether a participant was treated or not, he/she will be assumed treated for the purposes of analysis.

Pharmacodynamic Set

The PD analysis set will contain all participants from the randomised set who receive the appropriate dose of study treatment and have CMAP recorded for baseline and at least one post baseline assessment.

5 STATISTICAL METHODS/ANALYSES

The statistical analyses will be performed in accordance with ICH E9 guideline and guidelines presented in section 8.

5.1 General Considerations

All statistical analyses will be performed using the Statistical Analysis System® software version using SAS® (Statistical Analysis System) Version 9.4 or higher.

5.1.1 *Outputs Presentation*

5.1.1.1 *Tables Header*

Depending on the type of data, the summary tables will be presented as follows:

- For disposition, demographic and baseline data: by study intervention group and overall,
- For safety data and pharmacodynamic data: by study intervention group.

5.1.1.2 *Presentation of Study Intervention Group*

Tables, Figures and Listings (TFLs) will be displayed using the following study intervention group labels, in the order presented:

- Dysport 40 U
- Botox 16 U
- Xeomin 16 U

5.1.1.3 *Presentation of Visits / Timepoints*

Summaries by visit will be presented using visit number as collected in the electronic Case Report Form (eCRF).

Visits in the TFLs will be presented as follows and in the following order.

Table 2: Analysis visit and short name

Analysis Visit	Short Name
Screening	Scr
Baseline	Bsl
Day 7	D7
Week 4	W4
Week 8	W8
Week 12	W12
Week 16	W16
Week 20	W20
Week 24	W24
Week 28	W28
Week 32	W32
Week 36	W36
Week 40	W40

5.1.2 Descriptive Statistics

All raw and derived variables will be listed and described using summary statistics. For categorical variables, summary statistics will be displayed using descriptive statistics by frequency count and percentages by category. The missing category will be presented if there is at least one missing category for at least one study intervention group. Except otherwise specified, participants with missing data will be included in the calculation of percentages. For quantitative variables, summary statistics will be displayed using descriptive statistics by number of observations, arithmetic mean, SD, median, minimum and maximum and 95% CI if needed. Frequency and proportion of missing data will be displayed.

5.1.3 Baseline value

Unless otherwise specified, baseline is defined as the last non-missing measurement taken prior to Investigational Medicinal Product (IMP) administration (including unscheduled assessments).

For the EDB CMAP, the baseline value used for the analyses will be the average of six measurements, the three measurements at screening and the three measurements at baseline.

5.1.4 Reference Start Date and Study Day

Reference start date is defined as the day of the IMP administration.

The day of the IMP administration will be Day 1. Study day will be calculated as:

- The difference between the event date and the reference date plus one day, if the event is on or after the reference date.
- The difference between the event date and the reference date, if the date of event is prior to the reference date.

Study day will appear in any listings where an assessment date or event date appears.

In case of partial or missing event date, study day will appear missing while any associated durations will be presented based on the imputations described in [appendix A1](#).

5.2 Randomisation, Disposition and Analysis Sets

A listing presenting randomisation details will be provided.

The following disposition summaries and listings will be provided:

- Summary table with the number and percentage of participants screened, screen failed, reason for screen failure, randomised, treated, completer, withdrawn and reason for withdrawal by study intervention group and overall on the screened analysis set,
- Summary table with the number and percentage of participants per visit on the randomised set,
- Summary table on duration of participant participation in the study and on the study follow-up duration on the randomised set. The definition of the duration of participant participation is from date of consent to the last study visit. The definition of the study follow-up duration is from date of administration to the last study visit.
- Listing of participant disposition on the randomised set,
- Listing of dates of visit including duration of participant participation and study follow-up duration for the randomised participants,
- Listing of screen failure participants with the criteria not met on the screened analysis set,
- Listing of withdrawal participants with reason for withdrawal on the randomised set.

The following summaries and listings will be provided on the randomised set:

- Listing of participants not meeting at least one inclusion criteria,
- Listing of participants fulfilling at least one exclusion criteria,
- Summary of the number and percentage of participants in each analysis set by study intervention group and overall, based on all randomised participants with reasons for exclusion from each analysis set,
- Listing including flag for exclusion from each analysis set and reason for exclusion from each set.

5.3 Protocol Deviations

An exhaustive list of major Protocol Deviations (PDs) that may occur during the course of the study is defined in the PDs plan. Major PDs will be determined before unblinding of the study, finalised during the blind data review and documented in a PDs list.

Following PDs summary and listing will be provided on the randomised set:

- Number and percentage of participants with major PDs by deviation category
- A listing of major PDs.
- A listing of major PDs potentially having an impact on primary efficacy analysis:
 - o Participant received the wrong study intervention (Mis randomisation)
 - o CMAP at Week 28 or Week 40 performed out of a specified time window (> +/- 2 weeks)

5.4 Demography and Other baseline characteristics

All demographic and baseline characteristics summaries and listings will be provided on the randomised set. No statistical comparison between study intervention groups will be performed.

Following summaries will be provided on:

- Demographic variables (refer to [appendix A2](#) for EudraCT age categories),
- Other baseline characteristics:
 - Height, weight and Body Mass Index,
 - Alcohol breath test, drug of abuse test,
 - 12-lead ElectroCardioGram (ECG),
 - Clinical laboratory test,

Listings will also be provided for all the variables listed above as well as for severe acute respiratory syndrome coronavirus 2 (SARS-COV-2) test and serology.

5.5 Medical history, BoNT and non-drug therapies, medications and surgical procedures

Medical and surgical history, prior BoNT therapies, non-drug therapies and surgical procedures will be coded using the latest version of Medical Dictionary for Regulatory Activities (MedDRA) in effect within IPSEN at the time of database lock. Medications will be coded using the latest version of World Health Organization-Drug dictionary in effect within IPSEN at the time of database lock.

Medication, non-drug therapies and surgical procedures start and stop dates will be compared to the date of the IMP administration to allow classification as either Prior only, Prior and Concomitant, or Concomitant only.

Prior (P)	Start and stop dates prior to the date of study treatment.
Prior and Concomitant (PC)	Start date before the date of study treatment and stop date on or after the date of study treatment.
Concomitant (C)	Start date on or after the date of study treatment.

Summary tables on prior medications/non-drug therapies/surgical procedures will include "P" only, summary tables on concomitant medications/non-drug therapies/surgical procedures will include "C" and "PC".

See detailed rules in [appendix A1](#) for classification of prior and concomitant medication/non-drug therapies, surgical procedures in case of partial/missing date.

The therapeutic class will correspond to the second level of Anatomic Therapeutic Class (ATC) code that is corresponding to the first 3 figures.

Following summaries, presenting count and percentages of participants will be provided on the randomised set:

- Medical and surgical history by primary System Organic Class (SOC) and preferred term (PT),
- Concomitant medications (PC, C) by ATC class and PN (ATC level 2),
- Concomitant non-drug therapies (PC, C) by primary SOC and PT,
- Concomitant surgical procedures (PC, C) by primary SOC and PT,

Listings will be provided for all the summaries listed above as well as for prior medications, prior BoNT therapies and prior non-drug therapies. These listings should include a flag indicating the category (P, PC, C) as described in the table above.

5.6 Compliance

Participants will receive study intervention directly from the investigator or designee, under medical supervision at the study site on Day 1. Therefore, participant compliance with study intervention is not expected to be an issue and no listing or summaries will be performed.

5.7 Pharmacodynamic evaluation

5.7.1 General Considerations

The PD set will be used for pharmacodynamic analyses.

A listing of all pharmacodynamic data (raw and derived) should be provided (see listing detail conventions in [appendix A3](#)). Descriptive statistics will be provided for all endpoints by study intervention group and timepoint.

For the EDB CMAP, three measurements of CMAP will be taken at each timepoint. For post-baseline measurements, the mean of these three measurements will be used to determine the parameter percentage relative to baseline in CMAP total amplitude, used in all summaries and analyses of the EDB CMAP related endpoints. Baseline value definition is given in [section 5.1.2](#).

5.7.1.1 Significance Testing and Estimations

All statistical tests will be two-sided at the 5% level of significance unless otherwise specified. Confidence Intervals (CI) will be 95%, unless otherwise specified in the description of the analyses.

5.7.1.2 Handling of Dropouts and missing data

Diligent attempts will be made to limit the amount of missing data and to follow-up all randomised participants to collect the primary and secondary pharmacodynamic endpoints for the statistical analysis.

The Mixed Model for Repeated Measures (MMRM) is implicitly handling missing data as Missing At Random (MAR) without explicit imputation. This missingness assumption appears meaningful given the long term pharmacodynamic effect of the investigated compounds: the effect of the drug will persist after discontinuation and is not expected, given baseline profile of the participant and assessments until the timepoint of discontinuation, to depend on whether the participant remains observable in the study or drops out.

In case of occurrence of a major PDs with the potential to interfere with CMAP total amplitude (see [Section 5.3](#)), CMAP data collected after the PDs will be ignored, and will be handled by the model as MAR. This implements a 'per protocol' analysis assessing the treatment difference occurring in case participants adhere to the protocol by using a hypothetical handling strategy for this ICE.

5.7.1.3 Statistical/analytical issues

Adjustments for Covariates

Not applicable.

Interim Analyses and Data Monitoring

Not applicable.

Multicentre Studies

This is a single-centre study.

Multiple Testing

To control for the family-wise type I error rate at the two-sided level $\alpha = 0.05$, a Hochberg -procedure will be applied to investigate the two null hypotheses $H_{0,db} : \delta_{db} = 0$ and $H_{0,dx} : \delta_{dx} = 0$. The testing procedure uses the following decision rules for the two p-values p_{db} and p_{dx} :

- Both null hypotheses are rejected if $\max(p_{db}, p_{dx}) \leq \alpha$
- Only the null hypothesis corresponding to the smaller p-value $\min(p_{db}, p_{dx})$ is rejected if $\min(p_{db}, p_{dx}) \leq \alpha/2$ and $\max(p_{db}, p_{dx}) > \alpha$.

If both null hypotheses of the primary endpoint are rejected, then the same Hochberg procedure will be applied sequentially to the two respective null hypotheses comparing Dysport with Botox and with Xeomin for secondary endpoints in the following order:

4. CMAP total amplitude at Week 40 post-injection
5. Incidence of recovery of CMAP total amplitude at Week 28 post-injection
6. Incidence of recovery of CMAP total amplitude at Week 40 post-injection

The two null hypotheses of secondary endpoint k , $k = 2, 3$ are tested with a Hochberg procedure, when both null hypotheses of endpoint $k-1$ are rejected.

Convergence of the MMRM Model

If the default Newton-Raphson algorithm used by statistical analysis software PROC MIXED fails to converge, the Fisher scoring algorithm up to iteration 2 will be used (via the SCORING=2 option of the PROC MIXED statement) to obtain the initial values of covariance parameters [Mallinckrodt 2008]. If this alternative also fails to converge, then in addition the no-diagonal factor analytic structure (via the TYPE=FA0(T) option of the REPEATED statement, where T is the number of post baseline measurement timepoints incorporated in the MMRM analysis) will be used, which effectively performs the Cholesky decomposition of the covariance matrix and is numerically more stable.

When the above strategies fail, then, in addition to the changes described above, a model with the less complex heterogeneous Toeplitz covariance structure (TOEPh) will be fitted. When the above strategies fail, then, in addition to the changes described above, a model with the less complex compound symmetry covariance structure (CS) will be fitted. When all above measures fail, then the primary endpoint, CMAP total amplitude at Week 28, measured as percentage relative to baseline (%), will be analysed using an Analysis of Covariance (ANCOVA) model with covariates treatment and baseline CMAP amplitude.

The first algorithm that leads to convergence in this sequence of fallback measures will be the algorithm used for the primary analysis of the study.

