For EudraCT results summaries, in addition to quantitative descriptive statistics of age, demographic tables should include presentation of age using the following EudraCT categories (as applicable):

In utero
Preterm newborn - gestational age < 37 weeks
Newborns (0-27 days)
Infants and toddlers (28 days-23 months)
Children (2-11 years)
Adolescents (12-17 years)
Adults (18-64 years)
From 65 to 84 years
85 years and over

A3. Programming Convention for Outputs

All text fields must be left justified and numeric or numeric with some text specification (e.g.: not done, unknown, <4.5, ...) must be decimal justified.

The mean, median, lower quartile, upper quartile, SD, SE of the mean will be reported to one decimal place greater than the raw data recorded in the database.

The minimum and maximum values will be reported with the same number of decimal places as the raw data recorded in the database.

In general, the maximum number of decimal places reported should be four for any summary statistics.

Percentages will be presented to one decimal place. Percentages will not be presented for zero counts. Percentage will be calculated using n as denominator. The denominator n will be specified in a footnote for clarification if necessary. If sample sizes are small, the data displays will show the percentages, but in the CSR only frequency counts could be described.

P-values will be reported to four decimal places (e.g.: p=0.0037), after rounding. P-values which are less than 0.0001 will be presented as '<0.0001'.

Dates will be presented in the format [ddmmmyyyy] and times in the format [hh:mm].

A4. SAS code**a. MMRM analysis**

The SAS code for the MMRM is the following:

CCI

Where AVISITN includes all post-baselines visits when CMAP is measured, CMAPBL is the baseline of CMAP total amplitude and AVAL is the percentage relative to baseline of CMAP total amplitude (%).

If the PROC MIXED fails to converge, the first algorithm that leads to convergence in the following sequence of fallback measures will be the algorithm used for the primary analysis of the study:

- 1) Addition of scoring option

CCI

- 2) Addition of the no-diagonal factor analytic structure (via the TYPE=FA0(T) option of the REPEATED statement

CCI

- 3) Use of Toeplitz covariance structure

CCI

- 4) Use of compound symmetry covariance structure

CCI

CCI

CCI

5) ANCOVA model with covariates treatment and baseline CMAP amplitude

CCI

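### If the primary model falls back to homogeneous compound symmetry, the Week 28 standard error can be wrong in either direction; a heterogeneous version would largely remove this at little cost

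*SAP*

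**What the plan says.** SAP 5.7.2.2 fits a mixed model for repeated measures to percent of baseline at 11 visits (Day 7 to Week 40), with treatment, visit, their interaction, baseline amplitude and an unstructured covariance.

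For non-convergence, SAP 5.7.1.3 sets an order: Fisher scoring for starting values (SCORING=2), the FA0(T) parameterisation, heterogeneous Toeplitz (TOEPH), then "a model with the less complex compound symmetry covariance structure (CS) will be fitted", and last an ANCOVA of the Week 28 value on treatment and baseline. The first step that converges is the primary analysis. Protocol 9.4.2.3 has the same order. SAP Appendix A4 lists as its fourth step "Use of compound symmetry covariance structure"; the code beneath is redacted.

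The two primary comparisons are tested by a Hochberg procedure, "To control for the family-wise type I error rate at the two-sided level" of 0.05. SAP 5.7.3.2.1 analyses Week 40, the first key secondary endpoint, with the same model. SAP 5.7.2.3 plans no sensitivity analysis. The visible text names no empirical (sandwich) standard error and no degrees-of-freedom method for the CS step.

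**The concern.** The plan starts from a covariance in which each visit has its own variance, and its first simplification, heterogeneous Toeplitz, keeps that feature. The next step drops it. CS estimates one variance pooled from Day 7 to Week 40 and uses it for the Week 28 contrast. If the spread of percent of baseline changes as the muscle is inhibited and recovers, the Week 28 standard error reflects the average visit and not Week 28.

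CS has only two covariance parameters and will nearly always converge, so the Week 28 ANCOVA placed after it, which estimates the Week 28 variance directly, would hardly ever be used. The primary p-values, the 95% confidence intervals and the Week 40 key secondary would then rest on a variance assumption that nothing in the documents supports, and no planned sensitivity analysis would show it.

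**Working it through.** **Inputs from the documents.** SAP 2.2: "A total of 45 participants will be randomised in a balanced ratio of 1:1:1", so 15 per arm. SAP 2.3 on test and power: "Using a 2-sided t-test at the 5% significance level, the chosen sample size provides at least 88% power". The assumed Week 28 effect is 18 percentage points, and the SD is taken as common, "in all treatment arms of 15% as observed for Dysport in a legacy study". Joint success on both comparisons is put at 81% or more. No SD is given for any visit other than Week 28.

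**The plan's own figures.** True standard error of a Week 28 contrast: 15 × √(2/15) = 5.48. Noncentrality: 18 / 5.48 = 3.286. With 28 degrees of freedom the critical value is 2.048 and power is 88.7%, as stated. Simulating 400,000 trials with a shared Dysport arm gives 81.2% for both comparisons, also as stated.

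**Effect of CS.** With complete data the Week 28 point estimate is essentially unchanged, but its model-based standard error is based on the mean variance over visits:

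- R = (Week 28 SD) / √(mean of the 11 squared SDs)
- CS standard error ≈ true standard error / R
- per-test type I error ≈ 2 × [1 − Φ(1.96 / R)]

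Worked example with assumed SDs 12, 10, 10, 11, 12, 13, 14, 15, 15.5, 16, 16: the squares sum to 1951.25; divided by 11 this is 177.4, with root 13.32. R = 15 / 13.32 = 1.126, and type I error ≈ 2 × [1 − Φ(1.741)] = 0.082.

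**Simulation check.** 20,000 null trials per setting, complete normal data, exact REML fit of CS. Week 28 SD was fixed at 15. SDs at other visits were assumed, as was the correlation (AR(1) 0.85 or exchangeable 0.6). Degrees of freedom were 420 or Satterthwaite. Ranges cover both correlations and both choices of degrees of freedom.

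| Assumed SD profile | R | CS SE / true SE | Per-test type I error | Hochberg family-wise |
|---|---|---|---|---|
| Constant 15 | 1.00 | 5.5 / 5.5 | 0.051–0.053 | 0.048–0.053 |
| 10 at nadir, 15, then 16 | 1.13 | 4.9 / 5.5 | 0.082–0.085 | 0.086–0.092 |
| 5 at nadir, 15, then 18 | 1.24 | 4.4 / 5.5 | 0.115–0.118 | 0.129–0.134 |
| 8 at nadir, 15, then 24 | 1.02 | 5.4 / 5.5 | 0.056–0.059 | 0.054–0.059 |
| High at Day 7 and late | 0.89 | 6.2 / 5.5 | 0.028–0.030 | 0.023–0.026 |
| Early peak of 20–22 | 0.85 | 6.5 / 5.5 | 0.023–0.024 | 0.018–0.019 |

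The Week 28 ANCOVA gives 0.050–0.051 per test and 0.047–0.049 family-wise in every row.

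**Sensitivity to the late visits.** Take the nadir SD at Day 7 and Week 4, a linear rise to 15 at Week 28, and either a flat tail or a linear rise to 24 at Week 40. The approximation gives:

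| Nadir SD | Week 28, flat tail | Week 28, rise to 24 | Week 40, rise to 24 |
|---|---|---|---|
| 11 | 0.079 (R 1.11) | 0.042 (R 0.97) | 0.204 (R 1.54) |
| 8 | 0.104 (R 1.21) | 0.055 (R 1.02) | 0.231 (R 1.63) |
| 5 | 0.130 (R 1.29) | 0.068 (R 1.07) | 0.254 (R 1.72) |

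A late rise in SD therefore brings Week 28 close to nominal but moves the error to Week 40. For Week 40, R has the Week 40 SD in the numerator.

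**Power when R is below 1.** By normal approximation, power is Φ(3.286 − 1.96) = 0.91 with the correct standard error and Φ(3.286 − 1.96/0.851) = 0.84 at R = 0.85.

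**The case against.** The strongest case on the other side has four parts.

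- **Direction.** A reader might infer that CS, once reached, must understate the Week 28 standard error, because amplitude near zero at the nadir leaves little room to vary. That is a reasonable premise, but no visit-specific SD in either document supports it. The same reasoning, more spread during recovery, could raise the SDs at Weeks 32 to 40 and cancel the effect at Week 28. This objection stands: the bias can go either way.
- **Likelihood.** Four earlier attempts must fail first. In a check with complete data, an iterated least-squares fit of the unstructured model converged in 300 of 300 datasets. That is not PROC MIXED and had no dropout, but it suggests that CS would rarely be needed. The documents give no probability. This stands as a limit on size.
- **Redaction.** The A4 code could contain an empirical standard error. The figures above hold only for a model-based one. This stands.
- **Order.** Trying a likelihood model before ANCOVA is defensible, because it keeps participants without a Week 28 value under the missing-at-random assumption on which the estimand relies. This stands against simply deleting the step, but it is no argument for a common variance, since a heterogeneous structure keeps the same advantage.

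**Conclusion.** The point holds as a conditional, minor defect. Both documents place homogeneous CS ahead of ANCOVA and let it become the primary analysis. With a model-based standard error, its Week 28 inference is right only if the Week 28 variance happens to equal the average over visits. Under assumed profiles, per-test type I error is about 0.08 to 0.13 for R of 1.1 to 1.3, about 0.05 with constant variance, and about 0.02 with lost power for R near 0.85. Week 40 could reach about 0.20 to 0.25 if the SD rises to 24, although that test is made only after both primary hypotheses are rejected.

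A reader might infer that the trial's 5% family-wise error fails. The documents do not support that, because these rates apply only if the step is reached. As an illustration, if CS were used 2% of the time (assumed) at a family-wise rate of 0.13 and 0.05 held otherwise, the overall rate would be 0.98 × 0.05 + 0.02 × 0.13 = 0.0516.

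The results rest on assumed SDs and correlations, normal errors and complete data. With dropout, CS could also affect the estimate itself; this was not computed.

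**What to change.** Replace CS by heterogeneous compound symmetry (CSH) in protocol 9.4.2.3, SAP 5.7.1.3 and SAP Appendix A4, before unblinding, and keep ANCOVA as the last step. State the degrees-of-freedom method and the type of standard error in the text. CSH serves both Week 28 and Week 40 and keeps participants without a Week 28 value.

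The cost is one line and a few parameters: 12 for CSH (11 variances and one correlation), against 2 for CS, 21 for heterogeneous Toeplitz and 66 for unstructured. CSH may itself fail to converge, in which case the planned ANCOVA applies; since that text covers only Week 28, a matching sentence for Week 40 would help.

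CSH still assumes one common correlation. Its large-sample limit when the true correlation is AR(1) 0.85, found by minimising log|V| + tr(V⁻¹Σ) over CSH matrices V for true covariance Σ, gives a Week 28 SD of 14.63 in place of 15. Then R = 15 / 14.63 = 1.025 and type I error is about 0.056. At Week 40, R is 0.935 and type I error about 0.036. Both hold for every SD profile tried, so the remaining error is small.
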